17.7.3 Pharmacodynamic effects (Part 2 only)

Oximeter pulse rates will be presented in descriptive summary tables and in mean plots over time for each IP.

The subjective parameters "craving", "satisfaction", "product-liking" and "intent to use again", measured by VAS, will be summarized for each IP using descriptive statistics during the IP use phase. Additionally, the relative and absolute change from baseline will be calculated for the subjective parameter "craving" for each IP.

To determine the maximum PD effect attributable to the IP, the highest recorded increase from baseline (E_{max}), time to first instance of E_{max} (T_{Emax}), the E_{max} from time 0 to 60 minutes ($E_{max0-60}$), and the time to reach $E_{max0-60}$ ($T_{Emax0-60}$) will be calculated for the pulse rates and presented using descriptive statistics.

CONFIDENTIAL 69(76)

For the subjective parameter "craving", the largest recorded decrease (E_{max}) will be calculated and presented using descriptive statistics.

For the subjective parameter "satisfaction", which does not have a baseline, the highest recorded value (E_{max}) and time to E_{max} will be calculated and presented using descriptive statistics.

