3.	To assess the pharmacodynamic (PD) effects, measured as pulse rate and subjective outcome measures, of the moist NP 6 mg, 11 mg, and 16.6 mg products and the comparator products, Swedish snus 18 mg and own brand snus product.	3a.	The difference between the moist NP 6 mg, 11 mg, and 16.6 mg products and the comparator products, Swedish snus 18 mg and own brand snus product, for the highest recorded increase (E_{max}), the time to E_{max} (T_{Emax}), the E_{max} from time 0 to 60 min ($E_{max0-60}$), and the time to reach $E_{max0-60}$ ($T_{Emax0-60}$) in pulse rate from baseline, measured using a pulse oximeter after IP use.	(Section 11.5.3.1)	See Section 17.7.3.
		3b.	The difference between the moist NP 6 mg, 11 mg, and 16.6 mg products and the comparator products, Swedish snus 18 mg and own brand snus product, for the largest recorded decrease (E _{max}) in the subjective parameter "craving" and the highest recorded value for "satisfaction", measured using a 100 mm visual analog scale (VAS) after IP use.	(Section 11.5.3.2)	See Section 17.7.3.
		3c.	The difference between the moist NP 6 mg, 11 mg, and 16.6 mg products and the comparator products, Swedish snus 18 mg and own brand snus product, for the subjective parameters "product-liking" and "intent to use again", measured using a 100 mm VAS 30 minutes after IP use.	(Section 11.5.3.2)	See Section 17.7.3.
4.	To evaluate the safety and tolerability of the moist NP 6 mg, 11 mg, and 16.6 mg products and the comparator products, Swedish snus 18 mg and own brand snus product.	4.	Frequency, intensity, and seriousness of adverse events (AEs).	(Section 11.5.4)	See Section 17.7.4.

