10.5 Investigational product use instructions

In Part 1 and Part 3, the subjects will use their own brand snus product (Part 1) or the selected NP (Part 3) *ad libitum* throughout the 14-day period.

In Part 2, a single dose will be given in the morning of each IP use visit (Visits 4-8). Subjects will keep the pouch/portion between their upper lip and gum for 30 minutes and will be

CONFIDENTIAL 42(76)

instructed not to eat or drink, chew gum, or brush their teeth for 30 minutes before, during use, and 30 minutes after the use of IP.

Subjects shall abstain from oral tobacco/nicotine products as well as smoking (cigarettes or ecigarettes) for at least 12 hours prior to each IP use visit. To this end, subjects will be instructed to abstain from such products from approximately 20:00 (8 pm) the day before IP use visits (Visits 4-8). All IP uses will be performed during the morning hours (08:00 to 12:00) to facilitate abstinence.

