11.5.3.2 Subjective parameters

Subjective parameters ("craving", "satisfaction", "product-liking", and "intent to use again") will be rated using VAS, anchored with "not at all" to "extremely", or "very likely" for the "intent to use again" parameter.

The "craving" parameter will be assessed with the question "Right now, how strong is your urge to snus?" at the same pre-defined time points as the pulse rate assessments: -10 min prior to IP use, and 5 min, 10 min, 15 min, 20 min, 30 min, 40 min, 60 min, 1 h:30 min, 2 h, 4 h, and 6 h post-use.

The "satisfaction" parameter will be assessed with the question "Right now, is the product satisfying?" at the pre-defined time points: 5 min, 10 min, 15 min, 20 min, 30 min, 40 min, 60 min, 1 h:30 min, 2 h, 4 h, and 6 h post-use.

In addition, "product-liking" and "intent to use again" parameters will be assessed at 30 minutes post-use with the questions "How much did you like the product?" and "How likely are you to use this product again in the future?", respectively.

Time points for each of the VAS questions are outlined in Table 8.1-2, and allowed deviations from actual time are outlined in Table 11.1-1.

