17.1 General

Continuous data will be presented in terms of evaluable and missing observations, arithmetic mean, standard deviation (SD), median, minimum, and maximum value, Q1-Q3 (interquartile range [IQR]).

Categorical data will be presented as counts and percentages. When applicable, summary data will be presented by IP, and by assessment time. Individual subject data will be listed by subject number, IP, and, where applicable, by assessment time.

All descriptive summaries and statistical analyses will be performed using SAS Version 9.4 or later (SAS Institute, Inc., Cary, NC, US). The PK parameters will be calculated by non-compartmental analysis using the software Phoenix WinNonlin® version 8.3 or later (Certara Inc., Princeton, NJ, US).

For Part 2, baseline will be defined as the last data collection point prior to each IP use.

No adjustment for multiple comparisons will be performed. All formal comparisons will be made toward a designated reference product and all significant findings will be reviewed for medical relevance.

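### Craving relief (endpoint 3b) is defined as a between-product difference but only summarised per product as change from one pre-use VAS reading, so chance variation in pre-use craving adds avoidable noise

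*Protocol*

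**What the plan says.** - **Endpoint.** Protocol section 7.2, endpoint 3b, opens with "The difference between the moist NP 6 mg, 11 mg, and 16.6 mg products and the comparator products, Swedish snus 18 mg and own brand" product. For craving the quantity is the largest recorded decrease, "measured using a 100 mm visual analog scale (VAS) after IP use".
- **Analysis.** Section 17.7.3 says that "the relative and absolute change from baseline will be calculated for the subjective parameter" craving for each product, and that "the largest recorded decrease (E_{max}) will be calculated and presented using descriptive statistics". It names no model, confidence interval or covariate for craving.
- **Baseline.** Section 17.1 states: "For Part 2, baseline will be defined as the last data collection point prior to each IP use". For craving, section 11.5.3.2 and Table 8.1-2 schedule one pre-use reading, 10 minutes before use.
- **Design.** Section 9.9 allocates subjects to ten Williams sequences of five products. Section 10.5 has subjects "instructed to abstain from such products from approximately 20:00 (8 pm) the day before IP use visits (Visits 4-8").
- **Contrast with other secondary endpoints.** Sections 17.7.1 and 17.7.2 apply the mixed model of section 17.6.1 to nicotine extraction and to the continuous PK parameters. Section 17.7.3 does not.

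**The concern.** Craving Emax is the visit's pre-use score minus the lowest later score. If a subject arrives with more craving on the day of one product than on the day of another, the two Emax values differ even when the products work equally well. In the extreme, two products that both abolish craving differ in Emax only by the pre-use scores.

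Because endpoint 3b is itself a difference between products, readers will compare the per-product Emax summaries, and this visit-to-visit variation then sits inside the comparison. The pre-use score that could remove part of it is collected at every visit but is used only for subtraction. At stake is how clearly the study can show, or rule out, a difference in craving relief between the pouches and the two snus comparators.

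**Working it through.** **No craving figure to reproduce.** The only computed size in the protocol is 45 evaluable subjects for AUC0-inf (section 17.2). It reproduces, taking a true ratio of 1. The within-subject log SD is √ln(1 + 0.33²) = 0.3215, and n = 2 × [0.3215 × (1.960 + 1.282) / ln 1.25]² = 43.6. A t-based calculation with 4(n − 1) degrees of freedom gives 45, and 45/0.85 rounds up to 53. I take only n = 45 from it.

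**Assumed inputs** (the protocol gives none for craving): pre-use mean 65 mm, between-subject SD 18, residual SD 9, two products relieving 70% and 60%, visit-to-visit SD of pre-use craving (σv) varied.

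**Step 1: the cap.** Emax = pre-use − lowest score, and the lowest score is at least 0, so Emax ≤ pre-use. A pre-use score of 10 mm allows at most 10 mm.

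**Step 2: what adjustment can remove.** Let the lowest score follow the visit's pre-use score within subject with slope β and residual SD σe. The within-subject Emax difference then has variance 2(1 − β)²σv² + 2σe². Adjusting for pre-use craving leaves 2σe².

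- Additive relief (the same fall in mm whatever the start) means β = 1, so nothing is removed.
- If pre-use and lowest scores have equal within-subject variance and correlation r, the adjusted-to-raw variance ratio is (1 − r²)/[2(1 − r)] = (1 + r)/2. At r = 0, 0.2, 0.4, 0.6 and 0.8 this is 50%, 60%, 70%, 80% and 90%.

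**Step 3: proportional relief.** Ignoring the limits of the scale:

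- raw variance = 0.1² × 18² + (0.7² + 0.6²)σv² + 2 × 9² = 3.24 + 0.85σv² + 162
- adjusted variance (slope 0.65 on the pre-use difference) = 3.24 + 0.005σv² + 162

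The SD of the estimated difference is the square root of variance/45. The simulated column (2,000 trials) keeps scores within 0–100.

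| σv (mm) | Raw variance | Adjusted variance | SD raw / adjusted (mm) | Removed | Simulated SD raw / adjusted (mm) | Removed |
|---|---|---|---|---|---|---|
| 5 | 186.5 | 165.4 | 2.04 / 1.92 | 11% | – | – |
| 10 | 250.2 | 165.7 | 2.36 / 1.92 | 34% | 2.30 / 1.89 | 32% |
| 15 | 356.5 | 166.4 | 2.81 / 1.92 | 53% | 2.73 / 1.92 | 51% |
| 20 | 505.2 | 167.2 | 3.35 / 1.93 | 67% | 3.28 / 1.93 | 65% |

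**Step 4: the cap remains.** A second simulation used 45 subjects, between-subject SD 20, visit SD 15, β = 0.4 and a true difference of 10 mm before the scale limits apply.

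| Mean pre-use (mm) | Estimated difference, raw / adjusted (mm) | Variance removed |
|---|---|---|
| 70 | 9.0 / 9.1 | 28% |
| 50 | 7.2 / 7.2 | 38% |
| 30 | 4.3 / 4.2 | 60% |

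Adjustment narrows the interval but leaves the estimate where it was. The shrinkage towards zero at low pre-use craving is a floor effect of the scale.

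**Step 5: relative change.** It is undefined at a pre-use score of 0. A 5 mm shift is 6% of 80, 25% of 20, 50% of 10 and 100% of 5. I simulated no true change, with the later score equal to the pre-use score plus noise of SD 20, whole-mm scores and zeros excluded. At pre-use mean 50 and SD 28, the mean relative change ran from about −11% to +40% (5th to 95th percentile). The median stayed within about −12% to +10%, and mean absolute change within −4 to +5 mm. At a pre-use mean of 65 mm, mean relative change ran only from about −10% to +11%.

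**The case against.** The strongest case against is that section 17.7.3 plans description only. No model exists from which a covariate was left out, and section 17 leaves technical detail to the SAP, which may contain such a model. It stands that nothing in 17.7.3 is miscalculated or forbids adjustment. It does not dispose of the point. The protocol words endpoint 3b as a difference and then assigns it a summary that does not estimate one, while neighbouring secondary endpoints receive the within-subject model.

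Three stronger readings are tempting, and the protocol does not support them:

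- **Bias between products.** A reader might infer that products used on low-craving days are systematically disadvantaged. The Williams order, the common abstinence of at least 12 hours and the morning sessions balance pre-use craving across products in expectation. What remains is chance variation.
- **Adjustment as a cure for the cap.** Step 4 shows that the estimates are the same with and without it.
- **Relative change as an error to be deleted.** Endpoint 3b is an absolute decrease, and relative change is an additional summary. Section 17.1 also requires the median and quartiles, so a mean driven by a few low scores would be visible. If relief is proportional, the percentage scale is even the natural one. Whether to keep it is a matter of preference.

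It is also fair to object that the size of the gain is wholly assumed. With additive relief there is almost none, and with a visit SD of 5 mm it is about 10%.

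**Conclusion.** The point holds as a minor improvement in precision. Endpoint 3b asks for a between-product difference, and the planned summaries leave removable pre-use variation in any comparison made from them. The reduction in variance from adjustment lies between about 0% (additive relief) and 65% (proportional relief, visit SD 20 mm). In the proportional case the simulated reductions at visit SD 10, 15 and 20 are equivalent to about 1.5, 2.0 and 2.9 times as many subjects. These figures rest on assumed means, SDs and relief patterns, because the protocol gives none for craving. The primary analysis, the sample size and every decision rule are unaffected.

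**What to change.** Estimate the craving Emax differences for endpoint 3b with the within-subject mixed model of section 17.6.1 (product fixed, subject random), adding the visit's pre-use craving and the subject's mean pre-use craving as covariates. Work on the mm scale, since Emax can be zero and the log transformation of 17.6.1 would then fail. Report each difference with its confidence interval beside the planned descriptive tables, and note that a low pre-use score still limits Emax. Relative change may stay as a supplementary summary if it is read by its median and visits with a pre-use score of 0 are counted and shown as not calculable.

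The cost is a few sentences of analysis text and some programming. The pre-use score is already collected at every visit, so no data, visits or subjects are added.

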(SIS/TS 72:2020) and updated this standard in 2024 (SIS/TS 72:2024), maintaining the same limit. The German Federal Institute for Risk Assessment (BfR) recommended a limit of 16.6 mg/unit in their 2022 updated opinion (BfR Opinion no. 023/2022, 7 October 2022) [5].

Long- and short-term health effects of NPs are debated based on three key factors:

- Acute toxicity: The European Chemicals Agency's Committee for Risk Assessment (RAC) classifies nicotine as Acute Tox. 2 (oral) with the hazard warning 'H300: Fatal if swallowed' and an acute toxicity estimate of 5 mg/kg bodyweight. This classification is now enforced by EU Regulation 2018/1480.
- Addiction potential: Nicotine addiction potential is typically assessed through pharmacokinetic/pharmacodynamic (PK/PD) studies, where higher maximum observed plasma concentration (C_{max}) and shorter time to maximum (T_{max}) indicate greater addiction potential. Balancing this, products must achieve a sufficiently high C_{max} and short enough T_{max} to serve as viable alternatives for users of combustible cigarettes.
- Long-term health effects: Beyond addiction, concerns revolve around nicotine's long-term health impacts. Nicotine is associated with cardiovascular effects like temporary increases in heart rate (HR) and blood pressure [6, 7]. However, epidemiolocal studies have not conclusively linked snus use to cardiovascular disease onset, suggesting historical nicotine exposure levels among snus users may not significantly elevate the risk of developing cardiovascular disease.

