7.3 Exploratory objectives and endpoints

The exploratory study objectives and endpoints are presented in Table 7.3-1.

Table 7.3-1 Exploratory objectives and endpoints

No.	Exploratory objectives	No.	Endpoints ¹	Assessments	Analysis
1.	To evaluate the impact on "product-liking" vs. the subjects' usual Swedish snus product of choice by administering single doses of the moist NP 6 mg, 11 mg, and 16.6 mg	1.	Difference in "product-liking" vs. the subjects' usual Swedish snus product of choice between the moist NP 6 mg, 11 mg, and 16.6 mg products and the comparator product, Swedish snus 18 mg, measured on a 3-point scale using	(Section 11.6.1.1)	See Section 17.8.1.

CONFIDENTIAL 27(76)

	products and the comparator product, Swedish snus 18 mg.		a multiple-choice question (MCQ) 30 minutes after IP use.			
2.	To compare the nicotine extraction normalized PK parameters AUC _{0-inf} and C _{max} between the moist NP 6 mg, 11 mg, and 16.6 mg products and the comparator products, Swedish snus 18 mg and own brand snus product.	2.	Difference in nicotine extraction normalized AUC _{0-inf} and C _{max} between the moist NP 6 mg, 11 mg, and 16.6 mg products and the comparator products, Swedish snus 18 mg and own brand snus product.	(Section 11.6.1.2)	See Section 17.8.2.	
3.	To analyze the pattern of use during each of the two 14-day ad libitum usage periods of either own brand snus product usage or complete substitution with a moist NP product.	3.	Difference in the pattern of use during each of the two 14-day ad libitum usage periods of either own brand snus product usage or complete substitution with a moist NP product.	(Section 11.6.1.3)	See Section 17.8.3.	
4.	To compare the PK profile between the selected strength NP product and the usual brand snus product.	4.	To compare nicotine exposure (in Part 2), as measured by baseline-adjusted AUC_{0-inf} and C_{max} , between the selected strength NP product (in Part 3) and the usual brand snus product (in Part 1).	(Section 11.4.1)	See Section 17.8.4.	

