17.7.2 Pharmacokinetics of nicotine in plasma (Part 2 only)

The following non-compartmental PK parameters will be determined for each IP: AUC_{0-inf} , AUC_{0-last} , $AUC_{0-l.5h}$, C_{max} , T_{max} , and $T_{1/2}$. Where possible, both baseline-adjusted and non-adjusted PK parameters will be calculated.

 C_{max} and T_{max} will be derived from the observed nicotine plasma concentration data. AUC_{0-1.5h}, AUC_{0-last}, and AUC_{0-inf} will be calculated using log-linear trapezoidal interpolation. Calculations will be based on the actual sampling times recorded during the study. Concentrations below the lower limit of quantification (LLOQ) occurring before C_{max} will be treated as zero. Concentrations below LLOQ occurring after C_{max} will be omitted from the analysis. All baseline-adjusted PK parameters will be corrected for nicotine plasma concentrations at baseline (pre-use).

AUC_{0-inf} will be calculated as described in Section 17.4 above.

The continuous secondary PK parameters (i.e., all of the above except T_{max}) will be analyzed for both non-baseline-adjusted, and baseline-adjusted concentrations using the same model as described in Section 17.6.1 to assess non-inferiority between each test product and each comparator product respectively.

In addition, descriptive statistics for secondary PK parameters and concentrations (baseline-adjusted and non-baseline-adjusted) will be presented. PK plasma concentration curves over time will be presented.

All data will be listed by subject number.

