17.8.3 Ad libitum pattern of use (Part 1 and Part 3)

The pattern of use during the 14-day *ad libitum* usage periods will be summarized descriptively. This summary will include information on the total number of pouches/loose snus used per day, the estimated usage time per pouch/loose snus, and whether the subjects opened a new can each day. Additionally, the pattern of use data will be listed for both the own brand product period (Part 1) and the selected NP product during Part 3.

Additionally, the subgroup "loose snus users" will be analyzed and presented separately.

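### Tmax, the pharmacodynamic endpoints and the use-pattern endpoint are defined as differences, but Section 17 plans only descriptive summaries, with no paired contrast or interval

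*Protocol*

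**What the plan says.** **Endpoint definitions.** In Section 7.2, endpoints 2a and 3a-3c each open with "The difference between the moist NP 6 mg, 11 mg, and 16.6 mg products and the comparator products". Endpoint 2a covers the PK parameters, Tmax among them. Endpoint 3a covers pulse Emax, TEmax, Emax0-60 and TEmax0-60; 3b covers craving and satisfaction; 3c covers product-liking and intent to use again. In Section 7.3, exploratory endpoint 3 is the "Difference in the pattern of use during each of the two 14-day" ad libitum periods.

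**Planned analyses.** The tables in Section 7 point to 17.7.2, 17.7.3 and 17.8.3.
- Section 17.7.2 applies the mixed model to "The continuous secondary PK parameters (i.e., all of the above except" Tmax. What remains for Tmax is "descriptive statistics for secondary PK parameters and concentrations".
- Section 17.7.3 states that pulse Emax, TEmax and their 0-60 minute versions "will be calculated for the pulse rates and presented using descriptive statistics". The VAS measures are likewise summarised product by product.
- Section 17.8.3 states that the pattern of use in the two "usage periods will be summarized descriptively".

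**Stated purpose.** Section 6.1 says that a higher Cmax and a shorter Tmax "indicate greater addiction potential". Section 6.2 gives Part 2 the aim of judging addiction potential against snus through a PK/PD study, and Part 3 the aim of studying self-titration, including usage relative to Part 1. Section 8.2 justifies the crossover by each subject acting as their own control.

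**The concern.** An endpoint defined as a difference needs an analysis that yields the difference and its uncertainty. Here the definition and the analysis part company for one PK variable, all the pharmacodynamic variables and the use-pattern endpoint. Summaries by product or by period also discard the pairing for which the crossover was chosen: a reader cannot recover a within-subject interval from separate means and SDs without the within-subject correlation.

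At stake are the speed-of-uptake side of the protocol's own addiction-potential criterion, the pulse and subjective comparisons between pouches and snus, and the most direct evidence on whether users change how much or how long they use when they switch.

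**Working it through.** **1. Sections side by side.**

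| Endpoint | Defined as | Planned analysis |
|---|---|---|
| 2a, Tmax | difference, pouch vs comparator | excluded from model; descriptive (17.7.2) |
| 3a, pulse: Emax, TEmax, Emax0-60, TEmax0-60 | difference | descriptive per product (17.7.3) |
| 3b, craving, satisfaction | difference | descriptive per product (17.7.3) |
| 3c, liking, intent to use again | difference | descriptive per product (17.7.3) |
| Exploratory 3, use pattern | difference between periods | descriptive per period (17.8.3) |
| Exploratory 1, three-point question | difference vs the 18 mg snus | frequency table per product (17.8.1) |

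The last row shows that exploratory endpoint 1 has the same mismatch.

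**2. Is this detail left to the SAP?** No. Section 17 opens by saying it sets out the principal features. Where contrasts are wanted it specifies them: extraction (17.7.1), the other PK parameters (17.7.2), urine biomarkers (17.8.5) and daily exposure (17.8.6). For the rows above it specifies description, and for Tmax it expressly removes the model.

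**3. Extent in Part 2.** Secondary variables: Tmax (1) + pulse (4) + craving and satisfaction (2) + liking and intent (2) = 9. Product pairs: 3 pouches × 2 comparators = 6. So 9 × 6 = 54 defined comparisons have no planned interval.

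**4. What is covered.** Section 17.7.2 models Cmax and AUC0-1.5h for every pouch-comparator pair, with and without baseline adjustment. Section 17.8.5 tests equivalence of urine biomarkers between Part 3 and Part 1 and links the result to self-titration. Section 17.8.6 models daily exposure, which is extracted amount per unit × mean units per day. That product does not isolate behaviour: doubling extraction while halving units gives 2 × 0.5 = 1, the same ratio as no change in either. Units per day and minutes per unit have no contrast of their own.

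**5. Can the design support the missing intervals?** First the plan's own figure (Section 17.2: CV 33%, power 90%, 95% interval, bound 1.25; true ratio not stated, taken as 1).
- Log-scale SD = √ln(1 + 0.33²) = 0.3215; margin = ln 1.25 = 0.2231.
- N = 2 × 0.3215² × (1.960 + 1.282)² / 0.2231² ≈ 43.7, so 44. With the t distribution it is 45 (residual df 4(N−1)) or 46 (df N−1). The stated 45 is reproduced.
- 45 / 0.85 = 52.9, so 53 randomized, also reproduced.

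With 45 paired observations, the half-width of a 95% interval for a mean within-subject difference is t(0.975, 44) / √45 = 0.30 SD of the differences. The protocol gives no SD for these variables. For an assumed SD of differences of 10 to 30 units (mm on the VAS, or beats per minute), that is about 3.0 to 9.0 units.

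**6. What is lost by ignoring the pairing.** With equal variances and within-subject correlation r, unpaired SE / paired SE = 1/√(1 − r). The protocol gives no r. Assuming 0.5 gives 1.41, and 0.7 gives 1.83.

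**The case against.** A reader might infer that addiction potential and change in use are never estimated. The documents do not support that. Cmax and early exposure are modelled for every pair, Section 6.1 assigns no relative weight to Cmax and Tmax, and self-titration is tested through biomarkers and daily exposure.

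Nor do the 54 comparisons lack any estimate. With complete data, the difference between two product means equals the mean paired difference, so crude point differences can be read from the summary tables. What is missing is a paired contrast with its interval. The SE ratio in step 6 depends on an assumed correlation and on a reader differencing the summaries as if they were independent, which the protocol does not propose.

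The wording of the objectives also gives the sponsor some cover. Secondary objective 3 speaks of assessing pharmacodynamic effects, and exploratory objective 3 of analysing use; neither speaks of comparing. Description fits those verbs, and the endpoint wording could be loose drafting. That argument fails for Tmax, which falls under an objective to compare, and it does not remove the conflict with the endpoint column.

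Restraint has a case too: Section 17.1 makes no multiplicity adjustment, and many intervals on subjective measures in an open-label study invite selective reading. That bears on how the intervals are labelled, not on whether a difference-type endpoint should have one. Finally, a unit is not the same thing before and after the switch for the 10 to 15 planned loose-snus users, who move from self-prepared portions to pouches. That stands and shapes the fix.

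**Conclusion.** The mismatch is real and lies in the protocol text. Three secondary endpoints in full (3a-3c), one in part (2a, for Tmax) and exploratory endpoint 3 are not delivered as defined, and exploratory endpoint 1 shares the fault. In Part 2 that is nine secondary variables over six pairs without a within-subject interval; across Parts 1 and 3 it is the direct change in units per day and minutes per unit. The count follows from the protocol alone. The precision figures assume 45 complete pairs and the stated range of SDs; the SE ratio assumes equal variances and r of 0.5 to 0.7.

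The consequence is limited. The primary comparison and sample size are unaffected, and the wider aims are partly served by the modelled quantities. The point should be corrected, but it does not threaten the trial's main conclusion.

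**What to change.** - **Section 17.7.3:** for pulse Emax, Emax0-60 and the VAS measures, report the within-subject difference with 95% interval for each pouch against each comparator. Use the study's crossover mixed model on the untransformed scale, since changes from baseline and VAS scores can be zero or negative.
- **Sections 17.7.2 and 17.7.3:** for Tmax, TEmax and TEmax0-60, report a paired median difference (for example Hodges-Lehmann) with 95% interval. Leaving Tmax out of a log-scale model is reasonable for a variable tied to the sampling grid; leaving it without any contrast is not.
- **Section 17.8.3:** report the paired Part 3 minus Part 1 change in units per day and minutes per unit with 95% interval, showing pouch and loose-snus users separately. Section 7.3 already makes loose-snus users a subgroup for all exploratory endpoints.
- Label all of these as estimation, without multiplicity-controlled claims.
- For exploratory endpoint 1, add a paired contrast or reword the endpoint. If description is all that is wanted elsewhere, the Section 7 wording should be changed to match.

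The cost is a few sentences and additional tables, with no new data. The downside is a large set of unadjusted intervals, which the labelling must make plain.
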